**Low Intensity Focused Ultrasound of Medial Temporal Lobe
Regions for the Improvement of Learning and Memory /
Low Intensity Focused Ultrasound as a Non-Invasive Neural
Prosthetic for the Improvement of Emotion Regulation**

NCT03717922
Document Date: 12/8/2023

APPROACH

Participants. Participants will consist of 21 adults aged 35-90

Subject Recruitment. Participants will be recruited from the Human Connectome Project – Aging participant pool and through fliers placed around campus and greater Los Angeles.

Eligibility. Inclusion criteria: 1) age 35-90, 2) right handed, 3) English dominant language.

Exclusion criteria: contraindications for MRI (e.g. metal implants, pregnancy), history of head injury sufficient to warrant medical attention, history of alcohol or substance abuse or dependence, history of major psychiatric illness requiring treatment, history of cancer or other neoplastic syndromes, history of major neurologic illness (e.g. epilepsy).

Procedures.

Crossover Design. This study will be conducted using a crossover design in which each participant will complete two visits spaced two weeks apart. At one visit, they will receive LIFUP sonication to the right amygdala, and at the other, they will receive sonication to the left entorhinal cortex. The order of conditions will be randomized and counterbalanced across participants. Participants will be blinded to condition order, and all other testing will be conducted the same at both visits.

Screening. Participants who have consented to be contacted regarding future research projects will be contacted by study staff who will conduct a telephone screening to ensure eligibility.

fMRI and LIFUP administration. Prior to receiving LIFUP sonication, the LIFUP transducer will be aimed at the appropriate target region for the visit (either the amygdala or the entorhinal cortex) and gently strapped in place to their head. Participants will then return to the scanner where a T1 image will verify the position of the LIFUP transducer and allow for estimation of the spatial location of the sonication beam focus. If needed, adjustments to transducer placement will be made to ensure that the beam focus is correctly aimed; an additional T1 will be collected after adjustment. Once correct placement of the transducer has been confirmed, LIFUP will be administered in 10 sonifications at 650kHz, 720mW/cm, duty cycle 5% duration 30s, with 30s spacing between sonifications. LIFUP will be administered with a pulse repetition frequency of 10Hz for amygdala sonication and 100Hz for entorhinal cortex sonication. BOLD fMRI will be collected simultaneously during LIFUP administration.

MRI Data Acquisition. We will use a 3-Tesla Siemens PRISMA scanner. We will collect T1, T2, hi-res hippocampal T2, and diffusion-weighted structural images for each participant.

Additionally, we will collect arterial spin labeling and BOLD fMRI both before and after LIFUP, as well as BOLD fMRI during LIFUP administration. We will be using Human Connectome Project scan sequences to collect these images; detailed information about the protocols can be obtained here: <http://www.humanconnectome.org/documentation/Q1/imaging-protocols.html>.

Behavioral Testing. Participants will be administered the behavioral tests described below twice at each of their in-person sessions; once before LIFUP and once after LIFUP.

Verbal Free Recall Task. Verbal memory will be assessed using the Rey Auditory Verbal Learning Test (RAVLT) which involves repeated presentation of a list of 15 words. The order of RAVLT form administration will be randomized and counterbalanced across participants.

Spatial Navigation Memory Task. Participants will be presented with a computerized spatial arena simulating a museum art gallery. They will be instructed to learn the locations of three objects placed throughout the gallery. After the Learning Phase, the subjects will then be asked to locate the objects' shown location sans stimuli immediately after learning the set of locations of each object. After each learning phase, participants will complete an unrelated Distractor Task

within the task but unrelated to the Mission. The navigation and distractor task paradigm will be repeated three times. During the fourth and final trial, retrieval of spatial information during this trial will be measured as the distance between the location that participants selected and the true location of the object. Shorter distances will indicate better spatial memory performance. This assessment has four forms, the order of which will be randomized and counterbalanced across participants.

Brief Visuospatial Memory Test. In this test, the participant is presented with a 2x3 array of geometric figures for 10 seconds, then instructed to draw the figures from memory in the correct location on the page. The task consists of three learning trials, one long delayed recall trial, and one recognition trial. Learning performance will be calculated as the proportion of presented figures and figure locations successfully recalled during the initial presentations of the six-figure array. Long delayed recall memory performance will be calculated as the proportion of presented figures and figure locations successfully recalled freely after a 20-minute delay. Memory retention will be calculated as the proportion of presented figures successfully identified during a forced-choice recognition task. This assessment has 4 forms that will be used for repeat testing, the order of which will be randomized and counterbalanced across participants.

State Trait Anxiety Inventory. This is a questionnaire used to measure anxiety-like symptoms. The first half of the questionnaire asks about the degree to which several listed statements align with how a participant feel at the current moment (state anxiety). The second half asks about the degree to which the listed statements align with how a participant typically feels (trait anxiety).

International Affective Picture Stimuli Task. In this task, participants complete multiple trials in which a 15-second fixation cross is followed by a 2-second color-coded instruction for one of three trial types: WATCH (passively view a negative image), VIEW (passively view a neutral image), or REAPPRAISE (actively reappraise a negative image). The instruction image is followed by a 5 second presentation of a negatively or neutrally-valenced image. After each image presentation, participants rate their subjective level of current arousal and the degree of awfulness of the image (valence). The task consists of 24 VIEW trials, 24 WATCH trials, and 48 REAPPRAISE trials. Objective reactivity to each stimulus will be measured using galvanic skin response and heart rate. Emotional reactivity in this task will be quantified using the difference between negative and neutral stimuli (N-S). Emotional reappraisal will be quantified by taking the difference of the negative reappraisal stimuli and the negative stimuli (NR - N).

Data Analysis Plan.

Hypothesis 1a. LIFUP of the amygdala will decrease BOLD activation in the amygdala and functionally associated regions (e.g. DLPFC), as well as functional connectivity between the amygdala and connected regions. It will also increase perfusion in the amygdala. These changes will not be observed in response to LIFUP of the entorhinal cortex.

Hypothesis 1b. LIFUP of the entorhinal cortex will increase BOLD activation in the entorhinal cortex and functionally associated regions (e.g. DLPFC), as well as functional connectivity between the entorhinal cortex and connected regions. It will also increase perfusion in the entorhinal cortex. These changes will not be observed in response to LIFUP of the amygdala.

MRI Analysis. Analyses will be performed using FSL Version 5.0 (www.fmrib.ox.ac.uk/fsl). Stimulation-related functional data processing will include motion correction to the mean image, spatial smoothing (Gaussian Kernel FWHM = 8mm), high-pass temporal filtering ($t > 0.01$ Hz) and regression-based removal of outliers. Processing of rs-fMRI will include correcting for

motion artifacts (using framewise displacement calculations, DVARS and within-subject independent component analysis), scrubbing, slice timing, unwarping and spatial smoothing (Gaussian Kernel FWHM = 8mm). Functional data will be linearly registered to stereotaxic MNI space and co-registered with anatomic data for each participant. Processing of diffusion imaging will include correction for motion, eddy distortion and susceptibility induced distortion and then fitting diffusion tensors to the data, Subjects with greater than 3mm mean displacement will be excluded from analyses. Structural data (T1 and DTI) will be linearly registered to the standard MNI152 T1 2mm brain.

Stimulation-related fMRI Analysis. BOLD fMRI will be collected continuously during the LIFUP paradigms. A block-design model will be used to statistically compare the BOLD signal during LIFUP stimulation blocks to the BOLD signal during no-stimulation blocks. To examine effect of stimulation to target ROI activity, we will extract average BOLD response rates in both the targeted and control (non-targeted) region for each of the blocks and use mixed-effect models to compare activity during LIFUP conditions (on / off) within each ROI. To examine LIFUP-related network connectivity, we will use a seed-based approach and examine whole brain connectivity with the LIFUP target of interest and compare between stimulation (on-off) conditions using psychophysiological interaction modeling (PPI). To assess changes in connectivity in relationship to LIFUP, we will use dynamic connectivity to evaluate changes in ROI across each LIFUP condition. Finally, dynamic causal modeling will allow us to assess and compare how changes in activation in the LIFUP target may causally affect activation in other regions (e.g. increased amygdala activation leads to increased DLPFC activity).

RS-fMRI. We will compare the functional connectivity of the brain at rest before and after stimulation. Independent component analyses (ICA) will be used to statistically extract functional networks from each participant's rs-fMRI. Dual-regression analysis will then compare resting state networks between baseline and post-LIFUP to determine the effect of LIFUP on resting state functional connectivity. Age, sex and education will be included as additional regressors. Dual regression will also assess the association between these LIFUP-related longitudinal resting state network changes and emotional reactivity and memory performance.

Arterial Spin Labeling. Pulsed Arterial Spin Labeling (PASL) scans produce a perfusion image with voxel values representing local perfusion rates. For each subject, will be collected both before and after LIFUP. These PASL images will then be linearly registered to each subject's T1 structural image. Perfusion images will be processed by using the BASIL (Chappell et al., 2008) toolbox, including partial volume correction, then transferred to MNI space using non-linear registration in FSL. Then, a comparison of pre-vs-post tFUS sonication perfusion in the amygdala and entorhinal cortex will be conducted individually for each subject by subtracting the registered pre- sonication perfusion map from the post-sonication perfusion map. A 2×2 repeated measures analysis of variance (ANOVA), corrected for multiple comparisons using False Discovery Rate (FDR), will then be used to compare the longitudinal perfusion changes between amygdala sonication and ErC sonication.

Hypothesis 2. LIFUP of the amygdala will result in reduced subjective emotional reactivity to emotionally-salient stimuli compared to those presented before LIFUP; this reduction will not be observed with entorhinal cortex LIFUP.

Behavioral Analysis. Subjects, who will be unaware of the exact timing of the sonication onset, will be asked to report any unusual feelings, sensations or distress. To determine the effect of LIFUP on emotional reactivity, analyses of variance (ANOVA) will compare subjective valence

and arousal ratings between pre-LIFUP and post-LIFUP administrations of the IAPS task. Additionally, state and trait anxiety scores will be compared pre and post-LIFUP to determine LIFUP-related changes in anxiety levels.

Physiological Analysis. To determine the effect of LIFUP on psychophysiological reactivity to emotionally-salient stimuli, interbeat intervals (IBIs) will be calculated for each stimulus presentation using Autonomic Nervous System Laboratory (ANSLab). These IBIs in response to stimuli will be analyzed using multilevel modeling with a repeated measures within-subjects design, with target (amygdala / entorhinal cortex), timepoint (pre / post LIFUP), and instructions (view, watch, reappraise) included as model factors.

Hypothesis 3. LIFUP of the entorhinal cortex will result in better performance on memory tasks compared to both amygdala LIFUP and pre-LIFUP conditions.

Behavioral Analysis. To determine the effect of LIFUP stimulation on memory performance, performance on memory assessments before LIFUP, after entorhinal cortex LIFUP, and after amygdala LIFUP will be compared using ANOVA.

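### Blinding covers participants only; nothing masks whoever scores the drawn visuospatial recall, so part of the Hypothesis 3 contrast is open to scoring bias

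*Combined protocol and SAP*

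**What the plan says.** The Crossover Design section describes two visits per participant. At one, "they will receive LIFUP sonication to the right amygdala, and at the other, they will receive sonication to the left entorhinal cortex". On order it states: "The order of conditions will be randomized and counterbalanced across participants". The blinding provision is one sentence: "Participants will be blinded to condition order, and all other testing will be conducted the same at both visits". The Behavioral Analysis text under Hypothesis 2 adds only that subjects do not know exactly when sonication starts.

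Under fMRI and LIFUP administration, "the LIFUP transducer will be aimed at the appropriate target region for the visit (either the amygdala or the entorhinal cortex"), its position is checked on a T1 image, and the pulse repetition frequency differs by target (10 Hz for the amygdala, 100 Hz for the entorhinal cortex).

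The behavioral tests are given "twice at each of their in-person sessions; once before LIFUP and once after LIFUP". Three of them measure memory:

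- **Verbal recall.** "Verbal memory will be assessed using the Rey Auditory Verbal Learning Test (RAVLT) which involves repeated presentation of a list of 15 words".
- **Brief Visuospatial Memory Test.** Participants draw six figures from memory. Learning and delayed recall are each scored as the "proportion of presented figures and figure locations successfully recalled". A forced-choice recognition trial follows.
- **Spatial navigation.** A computerised task scored as a distance.

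Hypothesis 3 predicts better memory after entorhinal sonication than after amygdala sonication and than before sonication. The analysis is an ANOVA across those three conditions. The documents do not say who administers or scores any test.

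**The concern.** The blinding sentence is complete and names one group. Its second half standardises procedure across visits but masks nobody. Whoever aims the transducer or sets the pulse frequency must know the target, and the plan leaves that person free to score the tests.

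This matters most for the drawings, where someone must decide whether a figure, and its place on the page, counts as recalled. Hypothesis 3 is directional. A scorer who knew the condition and resolved doubtful drawings more generously after entorhinal sonication would move the result in the predicted direction. Such a shift looks the same in the data as a treatment effect. With 21 participants, a modest one could change the conclusion for the drawn scores.

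**Working it through.** **1. No figure to reproduce.** The documents give the sample size ("Participants will consist of 21 adults aged 35-90") but no alpha, power, effect size or SD. The arithmetic below shows sensitivity to scoring bias; it does not estimate how much bias there is.

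**2. Which memory measures are exposed.**

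| Measure | How it is scored | Exposure |
|---|---|---|
| Drawn learning and delayed recall | Figures and locations judged as recalled or not | Main exposure |
| RAVLT | Recalled words against a 15-word list; scorer not stated | Less, since a word is on the list or not |
| Forced-choice recognition | Correct identifications | Largely unaffected |
| Navigation | Computerised distance | Largely unaffected |

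**3. Why the design and analysis do not remove it.** Randomised, counterbalanced target order and test forms balance visit and form effects across the targets. A bias that follows the target or the pre/post label travels with the condition itself. If post-entorhinal scores are raised by an average of s points relative to the comparator, the expected contrast is the true effect plus s, and the ANOVA has no term that separates the two.

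**4. Size of one element.** Assume one point per figure and one per location; the plan does not spell this out.

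- Delayed recall, one trial: 6 + 6 = 12 elements. One element is 1/12 = 8.3 points on a 0–100 scale; half an element is 4.2 points.
- Learning, if scored over all three trials: 3 × 12 = 36 elements. One element is 1/36 = 2.8 points.

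**5. Effect on the false-positive rate.** Assumptions: a paired t-test of post-entorhinal against one comparator, n = 21 (20 degrees of freedom), two-sided 0.05, no true effect, and an SD of paired differences of 15 to 25 points.

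Standardised shift: b = s / SD. Noncentrality: b × √21. The rate is the probability that a noncentral t exceeds 2.086 in absolute value.

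| Average shift on delayed recall | b at SD 25 and SD 15 | False-positive rate |
|---|---|---|
| None | 0 | 0.05 |
| Quarter element (2.1 points) | 0.08 to 0.14 | 0.07 to 0.09 |
| Half element (4.2 points) | 0.17 to 0.28 | 0.11 to 0.23 |
| One element (8.3 points) | 0.33 to 0.56 | 0.31 to 0.68 |

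For the half-element row, 4.17/25 = 0.167 and 0.167 × 4.583 = 0.76, giving 0.11; 4.17/15 = 0.278 and 0.278 × 4.583 = 1.27, giving 0.23.

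One extra element over the 36-element learning score (2.8 points) gives b = 0.11 to 0.19 and a rate of 0.08 to 0.13.

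**6. Benchmark.** An observed mean difference of 2.086/√21 = 0.46 SD is enough for significance at this sample size.

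**The case against.** The strongest reply is that the documents are silent rather than wrong. They do not say that the people who place the transducer score the tests, that scorers see condition or timepoint labels, or that scorers know the direction of Hypothesis 3. A reader might infer all three, but the text supports only that nothing prevents them.

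Three other inferences also go too far.

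- **All of Hypothesis 3 is compromised.** Navigation and recognition need little judgement, and matching words to a 15-word list needs less than rating a drawing.
- **Large bias is likely.** An average over-credit of a whole element on delayed recall is an upper-end scenario with no support in the documents. On a three-trial learning score, one element is worth only a third as much.
- **Staff already in post could remove the bias.** The plan gives no staff numbers, roles or separation of duties. Masked scoring cannot undo an examiner's influence during testing, nor what an examiner wrote down live on the RAVLT; no audio recording is mentioned. Participants might also notice that the transducer sits on a different side at each visit.

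It is fair to add that order and forms are counterbalanced and that the comparator is an active sonication of another target. These limit order and form confounding, but they do not mask the scorer. A plan that leaves unmasked scoring of judged outcomes open, with a directional hypothesis, still has a gap that can be closed.

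**Conclusion.** The point holds for the drawn learning and delayed-recall scores. Followed as written, the plan permits unmasked scoring of these outcomes, and any bias that tracked target or timepoint would enter the Hypothesis 3 contrast in full. The RAVLT is less exposed, and the other memory measures hardly at all.

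The actual size is unknown. The half-element illustration (0.11 to 0.23 against a nominal 0.05) rests on the assumed SD, alpha, one-point-per-element scoring and a simple paired comparison in place of the ANOVA. It shows that a small average leniency would be enough to matter; it does not show that any occurred. The change is worth making because it is cheap, not because bias has been demonstrated.

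**What to change.** State who administers and who scores the RAVLT and the drawn test. Require the drawings to be coded, stripped of visit, target and pre/post labels, and scored in one batch after both of the participant's visits are complete. The pre/post label must go as well as the target, because Hypothesis 3 also compares with pre-sonication performance. The scorer should be a current team member who did not test that participant, where possible; whether staffing allows this is for the sponsor to confirm. Apply the same to the RAVLT only where verbatim or recorded responses exist.

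Drawings are lasting records, so any already scored unmasked can be coded and rescored.

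The cost is labelling work and later availability of scores. Sample size, visits and participant burden do not change. The change reduces scoring bias only: examiner influence during testing, and participants noticing the side of the transducer, should be acknowledged as remaining limits.

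### The between-visit contrasts compare two combined stimulation regimens and cannot attribute a difference to anatomical site

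*Combined protocol and SAP*

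**What the plan says.** The Crossover Design paragraph describes a "crossover design in which each participant will complete two visits spaced two weeks apart". The two conditions are fixed: "At one visit, they will receive LIFUP sonication to the right amygdala, and at the other, they will receive sonication to the left entorhinal cortex". Only their sequence is randomised: "The order of conditions will be randomized and counterbalanced across participants". The section on fMRI and LIFUP administration gives the shared settings ("LIFUP will be administered in 10 sonifications at 650kHz, 720mW/cm, duty cycle 5% duration 30s, with 30s spacing between sonifications") and then the one that differs: "LIFUP will be administered with a pulse repetition frequency of 10Hz for amygdala sonication and 100Hz for entorhinal cortex sonication". The document describes no sham, no second pulse rate at either target and no opposite-side condition. It gives no reason for the two pulse rates.

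The hypotheses are worded by structure alone. Hypothesis 1a lists the changes expected from amygdala sonication and adds: "These changes will not be observed in response to LIFUP of the entorhinal cortex". Hypothesis 1b makes the matching statement for the entorhinal cortex. Hypothesis 2 expects the fall in subjective reactivity to be absent after entorhinal sonication. Hypothesis 3 expects memory after entorhinal sonication to be better than after amygdala sonication. Pulse rate and side appear in no hypothesis and no model.

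Three planned analyses set one visit against the other:
- the repeated measures ANOVA of perfusion change (Arterial Spin Labeling);
- the multilevel model of interbeat intervals, which has target as a factor (Physiological Analysis);
- the ANOVA of memory scores (Behavioral Analysis under Hypothesis 3).

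**The concern.** Someone reading the hypotheses will take a significant target effect to mean that the structure sonicated made the difference. The design offers two other explanations that move in step with it: the side of the head and the pulse rate. Hypotheses 1a and 1b make this pressing, because they predict opposite BOLD directions for two conditions that also differ tenfold in pulse rate. If both predictions came true, comparing the visits could not say whether site, side or pulse rate set the direction. At stake is what a positive result may be said to show. The validity of the comparison between the two conditions as delivered is not in doubt.

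**Working it through.** The plan states no power, alpha or effect size, so there is no figure of its own to reproduce. The question is whether the effects are identifiable.

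**Inputs**

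| | Condition A | Condition B | Source |
|---|---|---|---|
| Site | amygdala | entorhinal cortex | Crossover Design |
| Side | right | left | Crossover Design |
| Pulse rate | 10 Hz | 100 Hz | fMRI and LIFUP administration |
| Duty cycle | 5% | 5% | same |
| Sonications | 10 of 30 s | 10 of 30 s | same |

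The sample size is from the Participants paragraph: "Participants will consist of 21 adults aged 35-90". Two visits each gives 21 × 2 = 42 visits.

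**Step 1: what the contrast estimates.** Let the within-participant difference between visits, after removing period, be D. Then

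D = (site effect) + (side effect) + (pulse-rate effect).

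Every A visit has all three indicators equal to 1 and every B visit has all three equal to 0. Their pairwise correlations are 1.00, and only the sum can be estimated.

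**Step 2: rank of the design matrix (one outcome per visit).**
- Participant (21 columns) and period (1): rank 22.
- Adding target: rank 23.
- Adding pulse rate and side as well: 25 columns, rank still 23.

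The last two columns add nothing. No covariate, mixed model or larger sample changes this.

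**Step 3: is the pulse-rate difference more than a label?** Pulse length is duty cycle divided by pulse rate.
- 10 Hz: 0.05 / 10 = 5 ms; 10 × 30 = 300 pulses per sonication; on-time 300 × 5 ms = 1.5 s.
- 100 Hz: 0.05 / 100 = 0.5 ms; 100 × 30 = 3000 pulses per sonication; on-time 3000 × 0.5 ms = 1.5 s.

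Total on-time is equal (10 × 1.5 = 15 s), but the pulse structure differs tenfold.

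**Step 4: illustration under assumed values.** Assume a two-sided 5% paired t-test with n = 21 (20 df), no site effect, and a side or pulse-rate effect that alone gives a standardised paired difference dz. The noncentrality is dz × √21.

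| Assumed dz | Noncentrality | Probability that the target test is significant |
|---|---|---|
| 0.3 | 1.37 | 0.26 |
| 0.5 | 2.29 | 0.59 |
| 0.8 | 3.67 | 0.94 |

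The nominal rate is 0.05. The document gives no basis for choosing among these values of dz, so the table shows how the problem scales and does not estimate a bias.

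**Step 5: which analyses are affected.**
- *Aliased:* the perfusion ANOVA, the target terms of the interbeat-interval model, and the contrast of post-entorhinal with post-amygdala scores in the memory ANOVA.
- *Not aliased:* BOLD on/off comparisons and the seed-based (PPI) connectivity analysis within a visit; resting-state networks before versus after; valence and arousal ratings before versus after. Each holds pulse rate and sonicated side constant.
- *But not a test of specificity either:* the Stimulation-related fMRI Analysis section extracts signal from a targeted and a control region, then compares on with off separately in each. It names no interaction. An effect found in one region and not in the other is not evidence that the two effects differ.

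**The case against.** The strongest reply is that each condition is openly defined by its own site, side and pulse rate, so the hypotheses can be read as shorthand for two regimens. On that reading the opposite BOLD directions may reflect a deliberate choice of pulse rates. This is a fair reading, and it makes much of the correction a matter of labelling. But the document does not say it, and the clauses that deny an effect at the other site are written about structures.

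The second reply is that within-visit data already carry regional information. This stands. Targeted and non-targeted regions in one visit share the same pulse rate and sonicated side, so a general effect of either would not by itself produce a response in one region only.

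A reader might also infer stronger things that the document does not support:
- *That the control region lies in the other hemisphere and so cannot help.* The hemisphere of the control region is never stated.
- *That every test under Hypotheses 1 to 3 is confounded.* The ANOVA of subjective ratings under Hypothesis 2 names only before versus after, and the connectivity analyses are on/off or before/after. For these the gap is that the specificity clause has no stated test.
- *That pulse rate or side is as likely an explanation as site.* The document gives no basis for ranking the three.
- *That comparing the sonicated structure with its mirror image would settle the matter.* That comparison tests laterality. It also mixes sonication with nearness to the transducer, and it does nothing for the behavioural hypotheses.

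On perfusion, the two factors of the 2×2 ANOVA are not spelled out. If one of them is region, its interaction with target would cancel any side or pulse-rate effect common to both regions. It would not cancel one that differs by region.

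**Conclusion.** The point holds for between-visit contrasts. In the perfusion ANOVA, the interbeat-interval model and the Hypothesis 3 memory ANOVA, site, side and pulse rate are aliased exactly (rank 23 with or without the extra terms), at any sample size. These analyses support a statement that two combined regimens differ. They do not support attributing the difference to anatomy, as Hypotheses 1a, 1b and 3 and the entorhinal clause of Hypothesis 2 do. The conclusion needs no numerical assumption. It rests only on the two conditions being delivered as described. How far a conclusion about site could mislead depends on side and pulse-rate effects that the document does not give.

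Within-visit contrasts are outside this criticism, though as planned they do not demonstrate site specificity. The change should be made before analysis. It concerns the claim and one model term, and gives no reason to regard the regimen comparison as invalid.

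**What to change.** Leave all stimulation parameters as they are.

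1. Restate the between-target parts of Hypotheses 1 to 3, and the target factor in the models, as right amygdala at 10 Hz versus left entorhinal cortex at 100 Hz. Limit the conclusions to a difference between regimens, and state that side and pulse rate cannot be separated from site. If the pulse rates were chosen to produce the predicted directions, say so in the hypotheses.
2. For the BOLD part of Hypothesis 1, replace the separate within-region tests by a region (targeted / non-targeted) × LIFUP (on / off) interaction within each visit. Specify the hemisphere of each region in advance. Hypothesis 1 also predicts changes in functionally associated regions, so state whether the non-targeted region is one of them. If it is, a null interaction would not refute the hypothesis.
3. Keep any mirror-image region as a sensitivity analysis only.

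This needs revised wording, one changed model term and defined region masks. It needs no new data, because BOLD is already collected during sonication. The price is a narrower headline claim: site specificity for Hypothesis 2, Hypothesis 3 and the between-visit perfusion comparison stays unidentified, and the report should say so.

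### Does the 24/24/48 trial split of the affective picture (IAPS) task give the WATCH condition too few trials?

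*Combined protocol and SAP*

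**What the plan says.** The section on the International Affective Picture Stimuli Task sets three trial types: VIEW (neutral picture, passive), WATCH (negative picture, passive) and REAPPRAISE (negative picture, active reappraisal). The counts are: "The task consists of 24 VIEW trials, 24 WATCH trials, and 48 REAPPRAISE trials".

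The same section defines two scores. For the first: "Emotional reactivity in this task will be quantified using the difference between negative and neutral stimuli (N-S"). The second is obtained by "taking the difference of the negative reappraisal stimuli and the negative stimuli (NR - N"). Because NR is named separately, N is most naturally the WATCH set. The letter S is not defined, but it can only stand for the neutral set.

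Hypothesis 2 concerns reactivity: "LIFUP of the amygdala will result in reduced subjective emotional reactivity to emotionally-salient stimuli", and "this reduction will not be observed with entorhinal cortex LIFUP". Its Behavioral Analysis states: "To determine the effect of LIFUP on emotional reactivity, analyses of variance (ANOVA) will compare subjective valence" and arousal ratings before and after sonication. It does not name the N-S score as the dependent variable. The Physiological Analysis models interbeat intervals by target and timepoint, with "instructions (view, watch, reappraise) included as model factors". Under Behavioral Testing, "Participants will be administered the behavioral tests described below twice at each of their in-person sessions", so each of the 21 participants takes the task four times over two visits.

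**The concern.** WATCH is the only condition that enters both scores, yet it has a quarter of the trials. REAPPRAISE enters one score and has half. The one hypothesis tied to this task concerns reactivity, and at equal trial SDs reactivity is the less precise of the two scores. With only 21 participants, a split that spends its trials in the wrong place could cost power for Hypothesis 2. Giving 8 of the 72 negative pictures the WATCH instruction instead of REAPPRAISE (24/32/40) would leave the number of trials, the pictures and the timings as they are, so it seems to offer precision for nothing.

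**Working it through.** **Inputs from the documents.** 24 VIEW, 24 WATCH and 48 REAPPRAISE trials (sum 96, of which 72 negative and 24 neutral); 21 participants; four administrations each. The documents give no SD, effect size, power or precision for this task, so there is no stated figure to reproduce or to fall short of.

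**Assumptions.** Trials are independent, and variances are in units of the WATCH single-trial variance. The VIEW:WATCH and REAPPRAISE:WATCH trial SD ratios are rv and r, both 1 unless stated. Tau is the SD between participants of the true change.

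**Step 1: trial level.** Var(N-S) = rv²/n(VIEW) + 1/n(WATCH), and Var(NR-N) = r²/n(REAPPRAISE) + 1/n(WATCH).

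- N-S: 1/24 + 1/24 = 0.0833 now; 1/24 + 1/32 = 0.0729 at 24/32/40, a fall of 12.5%. With rv at 0.5, 1.25 or 2 the fall is 20%, 10% or 5%.
- NR-N: 1/48 + 1/24 = 0.0625 now; 1/40 + 1/32 = 0.05625, a fall of 10%. The break-even is r² = (1/24 − 1/32)/(1/40 − 1/48) = 2.5, so r = 1.58. Above that the score gets worse (+5% at r = 2).
- REAPPRAISE mean: 1/48 to 1/40, a rise of 20%.
- REAPPRAISE minus VIEW: 1/48 + 1/24 = 0.0625 to 1/40 + 1/24 = 0.0667, a rise of 7%.

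**Step 2: group level.** More trials do not reduce true differences between people. Per person, the pre-post change in N-S has variance tau² + 2·Var(N-S). The amygdala-minus-entorhinal difference in that change has tau² + 4·Var(N-S), where tau is the SD of that difference.

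| Contrast | tau | 24/24/48 | 24/32/40 | Variance | SE |
|---|---|---|---|---|---|
| Pre-post | 0 | 0.1667 | 0.1458 | −12.5% | −6.5% |
| Pre-post | 0.5 | 0.4167 | 0.3958 | −5.0% | −2.5% |
| Pre-post | 1 | 1.1667 | 1.1458 | −1.8% | −0.9% |
| Between targets | 0.5 | 0.5833 | 0.5417 | −7.1% | −3.6% |
| Between targets | 1 | 1.3333 | 1.2917 | −3.1% | −1.6% |

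This is with all 21 on the new split. At tau = 0.5 the pre-post gain equals 21/0.95 = 22.1 participants instead of 21.

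**Step 3: partial use.** If only k of 21 use the new split, the variance falls by k/21 of the full fall. At tau = 0.5, pre-post, 10 of 21 give 5.0% × 10/21 = 2.4% (SE about 1.2%), and 5 of 21 give 1.2% (SE about 0.6%). The documents do not say how many participants have been tested.

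**Step 4: what cancels the gain.** A test depends on effect divided by SE. If 8 more passive negative trials per run made the true N-S effect 2.5% smaller (tau = 0.5) or 0.9% smaller (tau = 1), the pre-post gain would be gone. Nothing in the documents shows that the WATCH response would stay the same.

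**Step 5: does the gain reach the planned test?** If the Hypothesis 2 ANOVA uses N-S, yes. If it pools ratings over the 72 negative pictures, the variance of the mean is 1/72 under either split at equal SDs, and there is no gain. The text allows both readings.

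**Step 6: is 24/32/40 the right alternative?** At equal SDs, 24/36/36 does better on both scores (N-S −16.7%, NR-N −11.1%) but raises REAPPRAISE-mean variance by 33%. A 32/32/32 split gives N-S 0.0625 (−25%) and leaves NR-N at 0.0625, but needs 8 more neutral pictures. The choice depends on SD ratios that are not known and on how much weight reappraisal is given.

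**The case for a change.** The best case for the concern is that no hypothesis is stated for reappraisal, while reactivity carries Hypothesis 2 and is also related to network change in the resting-state analysis. Even so, reactivity has trial-level variance 0.0833 against 0.0625 for reappraisal. The plan gives no reason for 48 REAPPRAISE trials. Moving 8 of them lowers the reactivity variance at any VIEW:WATCH ratio, and the reappraisal variance too unless r exceeds 1.58. If each participant kept one split for all four administrations, the pre-post and between-target comparisons would stay within one version of the task.

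All of this arithmetic stands, and a statistician consulted before the first participant might well have raised it. What does not follow is that the plan falls short. The study's title names emotion regulation as an aim, reappraisal is the regulation measure in this task, and the interbeat-interval model keeps reappraise as a level, so a heavier REAPPRAISE allocation is defensible even though it is not explained. A switch part-way would leave two task versions aligned with enrolment time in a 21-person crossover, for a gain that the group-level figures put at a few percent of the SE at most once participants differ in their true response.

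**Conclusion.** The concern does not hold as an error. The split biases no contrast, contradicts no other statement in the plan and invalidates no test. It is one of several defensible ways to share 96 trials. The alternative would lower the pre-post SE by about 2.5% (tau = 0.5) or 0.9% (tau = 1) if all 21 participants used it, and by less for each participant already tested. The 6.5% figure needs tau = 0, that is, no true differences between participants in their change. Against this stand a 20% rise in REAPPRAISE-mean variance, a 7% rise for REAPPRAISE minus VIEW, and a possible shift in the WATCH response large enough to cancel the gain. The sign of the net benefit is therefore not established.

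These sizes rest on independent trials, equal trial SDs unless stated, the assumed values of tau, negative pictures that can be exchanged between instructions, and N read as the WATCH set.
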